10.7. Accrual estimates

This research study is looking for 100 participants and is only being conducted at Stanford.

10.8. Criteria for future studies

If data can be effectively co-registered, and initial models are promising, as evaluated by visual feedback from overlaid images and initial ROC analysis

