4. IMAGING AGENT/DEVICE/PROCEDURE INFORMATION

4.1. Device/Imaging Procedure: ExactVu

The following diagnostic procedures:

- In the operating room after time-out and anesthesia induction and immediately before radical prostatectomy or in the clinic immediately before biopsy, the EV29L transducer will be inserted in the subject's rectum. Cine sweeps will be performed to save images of:
 1. The entire prostate from posterior to anterior (may require 2 sweeps to cover base and apex)
 2. The peripheral zone using the highest zoom setting (30mm depth) on the system (may require 2 sweeps to cover base and apex).Analysis of these images will be performed after surgery but before prostatectomy or biopsy pathology is available. Reviewers will be blinded to prior biopsy pathology and imaging reports at time of analysis.

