9. MEASUREMENTS/ STATISTICAL CONSIDERATIONS

9.1. Primary outcome will be the prospective data collection of a consecutive series of biopsy and prostatectomy patients.

- PRIMARY OUTCOMES:
 - Evaluate the ability of micro-ultrasound to identify high grade prostate cancer foci (Gleason score ≥ 7) in comparison to final surgical pathology result (prostatectomy or biopsy)

9.2 Secondary outcomes will be an analysis of this data to identify or develop features that form a cancer prediction model

- SECONDARY OUTCOMES:
 - Evaluate the ability of micro-ultrasound to identify the borders of prostate cancer foci in comparison to final surgical pathology result in men after prostatectomy.
 - Evaluate the ability of micro-ultrasound to detect low grade prostate cancer foci (Gleason score 6)
 - Comparison of prostate cancer detection between micro-ultrasound and multiparametric magnetic resonance imaging (mpMRI).
 - Perform a detailed pathologic and imaging correlation between findings on micro-ultrasound, MRI and final surgical histopathology in men who undergo prostatectomy

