10. STATISTICAL CONSIDERATIONS

10.1. Statistical Design

This study is primarily exploratory, with the goal of collecting the initial correlative data between micro-ultrasound, conventional imaging, and pathology gold standard. As such, we are not intending to directly compare this imaging modality with standard of care, but rather to rigorously and prospectively collect this data in order to plan for larger, multi-institutional studies.

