10.5. Secondary Analysis

Goal will be to quantitatively co-register the micro-ultrasound data with MRI and pathology data, and apply advanced processing techniques such as machine learning or deep learning. Once an initial model is built to identify prostate cancer from micro-ultrasound, we will be able to design future studies.

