10.5.1. Analysis Population

The entire consecutive series will be analyzed

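### Could a prediction model with no signal look promising under Section 10.8 because the plan names no validation step?

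*Combined protocol and SAP*

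**What the plan says.** Section 9.2 describes the secondary work: "Secondary outcomes will be an analysis of this data to identify or develop features that form a cancer prediction model". Section 10.5 will co-register micro-ultrasound with MRI and pathology and "apply advanced processing techniques such as machine learning or deep learning". For the population, Section 10.5.1 says: "The entire consecutive series will be analyzed". Section 10.8, on criteria for future studies, is a conditional clause with no stated consequence. Its conditions are that co-registration works and that "initial models are promising, as evaluated by visual feedback from overlaid images and initial ROC analysis". On the use of the model, Section 10.5 says: "Once an initial model is built to identify prostate cancer from micro-ultrasound, we will be able to design future studies". Section 10.1 calls the study mainly exploratory, with data gathered "in order to plan for larger, multi-institutional studies".

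Section 2.1 adds that the team has already built predictive models from an MRI and pathology database and intends a similar method here. It does not describe how those models were validated.

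**The concern.** An ROC curve drawn on the men used to fit the model is biased upward, and the bias grows with the number of features relative to the number of men. Here the features are themselves to be found in the study data, the cohort is small, and the method may be deep learning. The ROC is the only quantitative element in Section 10.8. Read with no added step, the plan could let a worthless model appear promising, and a larger multi-institutional study could be planned on that footing.

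Two features of the design add to the worry. Features chosen before the folds are formed contaminate cross-validation. So does placing images of one man in both training and test sets, and under Section 4.1 each man contributes several sweeps ("Cine sweeps will be performed to save images of" the whole prostate and, at high zoom, the peripheral zone).

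**Working it through.** **1. What the text does and does not say.** Sections 2.1, 8.2, 9.2, 10.1, 10.3, 10.5, 10.5.1 and 10.8 are the places where a validation step could stand. None names one. The word 'validated' in Section 8.2 concerns data entry. Equally, none says that fitted values from the training men feed the ROC. Analysing the whole series is what cross-validation does: every man is used, and each is scored by a model that did not see him.

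**2. Men available.** Section 10.6 gives 68, for sensitivities of 77% and 90%, 80% power and alpha 0.05. A two-sided one-sample test gives

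n = [(1.960·√(0.77·0.23) + 0.842·√(0.90·0.10)) / 0.13]² = [(0.825 + 0.252)/0.13]² = 68.7,

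which agrees with 68 to within one man. Section 10.7 gives 100 participants, so both sizes are used below.

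**3. One label per man, no signal (all model inputs assumed).** With p independent noise features and groups of n₁ and n₀, the resubstituted AUC is roughly Φ(√[p(1/n₁ + 1/n₀)/2]). The simulated values come from a lightly ridged linear discriminant, 50% prevalence, 1,000 runs per cell, with 5-fold cross-validation by patient.

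| N | p | p(1/n₁+1/n₀) | Formula | Simulated, same men | Simulated, cross-validated |
|---|---|---|---|---|---|
| 68 | 5 | 0.294 | 0.65 | 0.648 | 0.501 |
| 68 | 10 | 0.588 | 0.71 | 0.717 | 0.497 |
| 68 | 20 | 1.176 | 0.78 | 0.815 | 0.495 |
| 100 | 5 | 0.200 | 0.62 | 0.621 | 0.498 |
| 100 | 10 | 0.400 | 0.67 | 0.677 | 0.498 |
| 100 | 20 | 0.800 | 0.74 | 0.759 | 0.504 |

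The formula runs low at larger p because it ignores estimation of the covariance. The direction of the bias is clear.

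**4. Many regions per man.** The outcomes in Section 9 concern foci and their borders, and Section 10.8 judges overlays, so labels are attached to regions. Assume 20 regions per man, 30% of them cancer, with labels independent within a man. At N=68 there are 68·20 = 1,360 regions, 408 positive and 952 negative, so 1/408 + 1/952 = 0.00350. At N=100 there are 600 and 1,400, so the sum is 0.00238.

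| p | Formula, N=68 | Simulated, N=68 | Formula, N=100 | Simulated, N=100 |
|---|---|---|---|---|
| 5 | 0.54 | 0.54 | 0.53 | 0.53 |
| 10 | 0.55 | 0.55 | 0.54 | 0.54 |
| 20 | 0.57 | 0.57 | 0.56 | 0.56 |
| 40 | 0.60 | 0.61 | 0.59 | 0.59 |

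None of these runs (200 per cell) reached 0.70. If labels cluster within men, the value with 5 to 20 features at N=68 is 0.58 to 0.65, and 0.70 is reached in 0 to 2% of runs.

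**5. Poorly done validation.** Choosing the best 5 of 20, 50 or 100 noise features outside the folds gives a cross-validated AUC of 0.65, 0.72 and 0.75 at N=68 (one label per man, 50% prevalence). Choosing inside the folds gives 0.50 to 0.51. With 40 noise features, 20 patches per man all carrying the man's label, and within-man correlation 0.5, splitting by patch gives 0.77 at N=68 and 0.72 at N=100. Splitting by man gives 0.50 and 0.51.

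**6. Price of a formal gate.** Suppose the cross-validated 95% lower limit had to exceed 0.50. With one real feature of AUC 0.75 (assumed, one label per man, 50% prevalence) among 5, 10 or 20 features, the rule passes in 80%, 68% and 38% of runs at N=68, so it rejects a real signal in 20%, 32% and 62%. At N=100 it rejects in 5%, 13% and 30%. A no-signal model still passes in 4 to 10% of runs.

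**The case for a change.** The best argument for a change is that 'they will cross-validate anyway' is incomplete. Step 5 shows that validation with selection outside the folds, or with a split by image, can make noise look useful. Both hazards are live here, because the plan intends to "identify or develop features that form a cancer prediction model" from study data and each man supplies many images. Visual review of overlays on training cases shares the same optimism. Planning the next study is also this study's declared purpose, and a sentence on patient-level folds would cost almost nothing.

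What stands is the direction of the bias, the importance of how validation is done, and the silence of the text. The region-level figures are not a ceiling either: strongly clustered labels, many features or a high-capacity network would raise them.

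What does not stand is the step from silence to a faulty method. Section 10.8 does not say which predictions feed the ROC. Splitting by patient, with selection and tuning kept inside the training part, is routine for people who build imaging models, and Section 2.1 describes a team that has built such models before. That is not proof of sound validation, but it weakens the inference that none is meant. Nor does the plan contain a threshold that noise could be shown to pass: every pass rate depends on a cut-off supplied from outside it.

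**Conclusion.** The concern describes a rule left unwritten rather than a wrong one. Used on its own training men, a no-signal model would show an AUC of roughly 0.54 to 0.57 (5 to 20 features, 20 regions per man, independent labels, 68 men), 0.58 to 0.65 with clustered labels, and 0.65 to 0.82 with one label per man. The documents give no number of features, prevalence or unit of analysis, so the size for the actual model is unknown.

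The consequence is limited. Under Section 4.1 the images are read before pathology is available, so a model trained on that pathology cannot enter the primary reading. No patient decision rests on the model, and Section 10.8 triggers no automatic step. A fixed statistical gate would be a questionable addition to an exploratory study, since at 68 men it would turn away a real AUC of 0.75 in 20% to 62% of runs. Whoever uses the AUC for later planning will need to know how the predictions were obtained. That is a matter for the analysis and its report, and the plan can stay as it is.

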3. PARTICIPANT SELECTION AND ENROLLMENT PROCEDURES

3.1. Inclusion Criteria

3.1.1. Patient scheduled for MR-US fusion prostate biopsy or radical prostatectomy

3.1.2. Ability to understand and the willingness to sign a written informed consent document.

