4.2 Procedure Details for Pre-Biopsy Patients

In subjects undergoing pre-biopsy ExactVu micro-ultrasound imaging of the prostate, the imaging will occur immediately before biopsy. Prior to imaging, risks and benefits will be discussed with patient and informed consent will be obtained. He will be placed in a left lateral decubitus position for imaging. The imaging protocol will be identical to that listed above for the pre-surgery micro-ultrasound imaging. After images are complete, the micro-ultrasound probe will be removed and the prostate biopsy will proceed. Apart from the micro-ultrasound imaging, the biopsy will proceed as normal including administration of a single dose antibiotics, a pre-procedure cleansing enema, imaging with a Hitachi Noblus Ultrasound Unit featuring a 7 mHz probe, peri-prostatic anesthetic block, and biopsy core acquisition.

Predicting Location and Extent of Prostate Cancer using Micro-Ultrasound Imaging

At the close of the procedure, the patient will be reminded of the signs and symptoms of urinary sepsis, urinary retention, and excessive bleeding. These risks are a result of the biopsy and are unchanged by the micro-ultrasound imaging.

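### The ROC behind the go criterion is not split by scan setting, so a pooled AUC can credit the model for recognising the setting or patient group rather than cancer

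*Combined protocol and SAP*

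**What the plan says.** All references are to the combined protocol and SAP.

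- **Who enters (3.1.1).** "Patient scheduled for MR-US fusion prostate biopsy or radical prostatectomy". The share of each group is not given.
- **Where they are scanned (4.1).** "In the operating room after time-out and anesthesia induction and immediately before radical prostatectomy or in the clinic immediately before biopsy". For the clinic scans, 4.2 adds: "He will be placed in a left lateral decubitus position for imaging". No position is stated for the operating-room scans.
- **What is common to both (4.2).** "The imaging protocol will be identical to that listed above for the pre-surgery micro-ultrasound imaging". Transducer and sweeps are therefore the same.
- **The model (10.5).** Micro-ultrasound is to be co-registered with MRI and pathology, and the team will "apply advanced processing techniques such as machine learning or deep learning". The section continues: "Once an initial model is built to identify prostate cancer from micro-ultrasound, we will be able to design future studies".
- **The model's population (10.5.1).** "The entire consecutive series will be analyzed".
- **The go criterion (10.8).** Data must be effectively co-registered and initial models must be promising, "as evaluated by visual feedback from overlaid images and initial ROC analysis". There is no AUC threshold, no ROC unit (man, region or voxel), no held-out set and no split by setting.

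**The concern.** Scan setting is fixed by the indication, and the indication is tied to the label. Men booked for radical prostatectomy are being operated on for cancer, and 9.2 takes it for granted that they have cancer foci to outline. Men booked for biopsy are still being diagnosed. If cancer is more common in the first group, any image feature that separates operating-room from clinic scans also separates cancer from non-cancer in the pooled data, even when it says nothing about cancer within either group.

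A machine-learning model is free to use such a feature. Perfect pathology would not prevent it. Cross-validation would not reveal it either, because the link between setting and label is present in every fold. At stake is the decision in 10.8: a pooled AUC could look promising and then fall in a later study that uses one scan setting.

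**Working it through.** **The plan's own figure.** The documents give no AUC to reproduce. The only computed figure is N=68 in 10.6. A two-sided one-sample test of 0.77 against 0.90 at alpha 0.05 and 80% power gives n = [(1.960·√(0.77·0.23) + 0.842·√(0.90·0.10)) / 0.13]² = 68.67, in line with the stated 68. This point does not dispute it.

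**Formula.** Let w be the share of surgery men, and pS and pB the cancer prevalence in surgery and biopsy men. Take a score that identifies the setting and nothing else.

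- Surgery share among cancers: c = w·pS / [w·pS + (1−w)·pB]
- Surgery share among non-cancers: n = w(1−pS) / [w(1−pS) + (1−w)(1−pB)]
- Pooled AUC = 0.5 + 0.5(c − n)

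If pS = pB, then c = n and the AUC is 0.50. Within one setting the score is constant, so its AUC is 0.50 wherever that setting has both cancers and non-cancers.

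**Inputs.** The two settings and the single population come from 4.1, 4.2 and 10.5.1. The values of w, pS and pB are assumptions.

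**Per-man results.**

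| w | pS | pB | c | n | Pooled AUC |
|---|---|---|---|---|---|
| 0.10 | 0.90 | 0.50 | 0.167 | 0.022 | 0.57 |
| 0.10 | 0.95 | 0.30 | 0.260 | 0.008 | 0.63 |
| 0.30 | 0.85 | 0.60 | 0.378 | 0.138 | 0.62 |
| 0.50 | 0.95 | 0.50 | 0.655 | 0.091 | 0.78 |
| 0.70 | 0.95 | 0.40 | 0.847 | 0.163 | 0.84 |

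The first two rows are the ends of the range for w = 0.10 with pS 0.90–0.95 and pB 0.30–0.50. Rows three and five are the ends for w 0.30–0.70 with pS 0.85–0.95 and pB 0.40–0.60. On those same prevalences, w = 0.10 gives 0.55 to 0.60.

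**Surgery prevalence of 100%.** The formula gives 0.83 at w = 0.50, pB = 0.50 (c = 0.667, n = 0) and 0.93 at w = 0.70, pB = 0.40 (c = 0.854, n = 0). There are then no non-cancers among surgery men, so the man-level AUC within surgery is undefined. These cases are left out of the stated range.

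**Voxel level.** The same formula applies, with pS and pB read as the fraction of voxels that are cancer. For assumed pairs of 5% v 4%, 5% v 2%, 5% v 1% and 10% v 2%, and w of 0.25 or 0.50, the AUC runs from 0.52 (w = 0.25, 5% v 4%) to 0.70 (w = 0.25, 10% v 2%). A wider gap than these pairs would give more.

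**A model with some real signal.** Let the AUC within each setting be 0.65, let the setting dominate the score, and take w = 0.50, pS = 0.90, pB = 0.40. The shares of all men are 0.45 and 0.20 for cancers (surgery, biopsy) and 0.05 and 0.30 for non-cancers. Pooled AUC = [0.65(0.45·0.05 + 0.20·0.30) + 0.45·0.30] / (0.65·0.35) = 0.1886/0.2275 = 0.83.

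**The case against.** The strongest case against has five parts.

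1. **The ROC is not the whole criterion.** Section 10.8 also requires co-registration and judges overlaid images. A score that only recognises the setting is constant within a man and localises nothing, so the overlay could expose it. This stands as a partial safeguard. It is subjective and has no rule, and a model that mixes weak signal with a setting effect could still give plausible overlays.

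2. **Pooling is inferred.** Section 10.8 does not say that one curve will be drawn, and two secondary outcomes in 9.2 are limited to prostatectomy men. This stands. But 10.5.1 is the only population given for the model, and nothing calls for results by setting, so the plan allows a pooled ROC.

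3. **The likely unit is not the man.** The title, the focus-based outcomes, the co-registration and the overlays all point to a region- or voxel-level model, where the effect is smaller. This stands, and the per-man figures should be read with it in mind. The effect remains wherever the positive share differs by setting.

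4. **The image shortcut is not shown.** The sweeps are identical, and no difference in gain, orientation or operating-room position is documented. This stands: a score that identifies the setting perfectly and carries no cancer information is a worst case. Identical sweeps do not make anaesthesia or surroundings equal.

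5. **The study is exploratory.** True, but 10.1 gives its purpose as planning larger studies, which is where a misleading ROC would do harm.

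A reader might infer that 10.8 decides on the ROC alone, that the model will in fact learn the setting, or that an AUC of 0.83 to 0.93 is to be expected. The documents support none of these. The first omits co-registration and the overlay, the second is a possibility only, and the third needs every surgery man to be a cancer and a per-man ROC.

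**Conclusion.** The point holds in a limited form. The documents establish two scan settings tied to indication, one model population, and an ROC in the go criterion that is not split by setting. A pooled AUC can therefore credit the model for recognising the setting or the patient group.

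The size is uncertain. For a setting-only score it is about 0.57–0.63 per man with 10% surgery men, about 0.62–0.84 with 30–70%, and about 0.52–0.70 at voxel level, all under the assumed prevalences shown. The higher prevalence in surgery men is expected from the indication and is not stated; with equal prevalence there is no inflation.

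This is a cheap improvement. It concerns the secondary model analysis and the go criterion, and leaves the primary sensitivity outcome and N=68 untouched.

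**What to change.** In 10.5 and 10.8:

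- Name one ROC unit for both settings. Region level is suitable because surgery men then contribute non-cancer units. The region must be defined so that pathology exists for it in both groups.
- Report the AUC within each setting next to the pooled AUC, with intervals that allow for several regions per man.
- Report the AUC of a score that uses scan setting alone, at the same unit, as a benchmark.
- State in 10.8 that a model is not called promising on a pooled AUC that the within-setting AUCs do not support.
- If a man-level ROC is also shown, give it within the biopsy group only where surgery men have too few non-cancers. For example, if half of 68 are surgery men and 95% have cancer, 34 × 0.05 = 1.7 non-cancers are expected. Do not average a man-level AUC from one group with a region-level AUC from the other, since they measure different things.

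The cost is a few sentences in the two sections and a few lines of code. Scan setting is already known for every man, so no new data are needed. The downside is wider intervals for the within-setting AUCs.

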Appendix A: Inclusion/Exclusion Criteria Checklist

*All subject files must include supporting documentation to confirm subject eligibility. The method of confirmation can include, but is not limited to, laboratory test results, radiology test results, subject self-report, and medical record review.

Inclusion Criteria (From IRB approved protocol)	Yes	No	Supporting Documentation*
1. -Scheduled for MR-US fusion prostate biopsy or radical prostatectomy			
2. -Agree to consent to the study			
Exclusion Criteria (From IRB approved protocol)			
1. -Does not agree to consent			

IV. Statement of Eligibility

This subject is [eligible / ineligible] for participation in the study.

Signature:	Date:
Printed Name:
